vaccination and one month post-vaccination. Maternal a maternal serum sample will be collected by hospital staff during the hospital stay at the time of delivery and we will obtain a sample of cord blood. Cord blood is standardly collected and stored following every delivery at OSUMC. If the sample is not needed for medical reasons, it is discarded after a few days. We will obtain samples that would otherwise be discarded. If maternal serum is not collected at the time of hospital stay due to error in coordinating with hospital staff, we will arrange for a serum sample to be collected at the participant's home, a visit to our laboratory or CRC, or we will coordinate with the woman to collect this sample at the time she nexts visits her physician for a post-partum visit. If cord blood is not available from the hospital due to not being collected at delivery or used for testing purposes for infant care, we will arrange for infant blood to be collected by heel stick at the participant's home, a visit to our laboratory or CRC.

B. Sample

Pregnant women ages 18 and older will be recruited. As a part of routine care, pregnant women are encouraged to receive influenza vaccination. Women will primarily be recruited at their regular prenatal or gynecology visits at McCampbell Clinic. Those who are interested will be asked questions related to inclusion/exclusion criteria (i.e. age, health conditions, medications, and fetal health) to determine if they are eligible. Participant medications and health status (e.g., presence of chronic health conditions) will also be determined via chart review to confirm eligibility. Eligible individuals will be consented and the study will be described verbally to them.

Inclusion criteria for participants are adult (18 years and older) pregnant women who choose to have the influenza vaccination and who give informed consent. Exclusion criteria are fetal anomaly, health conditions or medications with a major immune component (e.g., arthritis, cancer, lupus) and inability to give informed consent.

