Participants will be recruited from the prenatal clinic and general gynecology clinic at McCampbell Hall, OSU. Participants will also be recruited through flyers at other Ob/Gyn clinics and advertisements in local newspapers and campus newsletters (e.g., OSU Today) and ads posted online (e.g., on Campus newsletters; Stressandpregnancy.osumc.edu and other relevant websites for advertising/recruiting including ResearchMatch.org). Study visits will be completed at McCampbell Clinic, the OSU Clinical Research Center at Dodd Hall, or at [name] clinical laboratory at the Institute for Behavioral Medicine Research. If women are unable to travel to OSU for study visits (e.g., due to child care obligations), they may be given the option, funding permitting, of having a nurse or phlebotomist visit their home to complete follow up visits. (All Visit 1s will be conducted at either McCampbell Clinic or the CRC as this study visit requires the administration of the influenza virus vaccine).

C. Vaccination/ Measurement / Instrumentation

Influenza Vaccination. Each woman will be administered a standard influenza vaccine produced by GlaskoSmithKline or SanofiPasteur as available from the OSU Pharmacy which supplies McCampbell Clinic. The vaccine will be administered by a clinic nurse or a Clinical Research Center nurse. Each .05mL dose contains 45 µg of hemagglutinin of each of virus strain. All women vaccinated during the same influenza season will receive the vaccine from the same manufacturer and same lot whenever possible.

Serum samples. At each visit, whole blood will be collected into vacutainer tubes while the subject is in a seated position. Samples will be immediately centrifuged and placed in freezer storage until analysis. These samples will be stored at the laboratory of [name].

Self-report Measures. Questionnaire measures will be used assess how psychosocial factors (including stress, mood, and social support) relate to immune parameters of interest. Each of the following will be completed at one or more study visit.

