Analysis of influenza antibody titers. Antibody titers will be determined using an ELISA for the complete vaccine and each of the HA proteins included in the vaccine in the given year. Briefly, 96-well plates will be coated overnight at 4°C with vaccine (0.9 mg/ml) or purified HA protein (0.3 mg/ml), washed, and incubated 2 hr at 37°C; serum dilutions prepared in phosphate-buffered saline supplemented with 10% fetal bovine serum will then be added. Plates will be re-washed and goat anti-human IgG antibody and then alkaline phosphatase conjugate will be added and plates will be incubated 2 hr at 37°C. The secondary antibody will be detected using Sigma 10 phosphatase substrate tablets (Sigma) in diethanolamine buffer and absorbance was read at 405 nm. Titers were determined by identifying the serum dilution at which the titration curve became asymptotic.

Statistical Considerations.

Sample size calculation.

Sample size was based on ≥80% power to examine each hypothesis. Although Holm's stepdown procedure will be used in analyses, the more conservative Bonferroni adjustment was used for calculating sample size. For testing associations of composite stress and obesity with maternal antibody responses (Aim 1), our analyses will focus primarily on A/H1N1 and secondarily on influenza B; a 2009 meta-analyses concluded that responses to A/H3N2 strains are generally not susceptible to stress.[10] A

sample size of 60 in a given year will provide $\geq 90\%$ power to detect an odds ratio of 0.4 for 4-fold antibody increase for one SD increase in composite stress, at the Bonferroni-adjusted significance level $\alpha=0.025$. A sample size of 180 across 3 years will provide $\geq 82\%$ power to detect an odds ratio of 0.38 for obese vs. non-obese, also at $\alpha=0.025$. These effect sizes are shown in our preliminary data. We will have $\geq 80\%$ power to detect these effects for influenza B, assuming similar effect sizes. For testing associations of composite stress and obesity with cord blood antibody levels (Aim 2), a sample size of 60 in a given year will provide $\geq 80\%$ power to detect an odds ratio of <0.45 for adequate cord blood antibody level for one SD increase in composite stress, at $\alpha=0.025$. A sample of 180 across 3 years will provide $\geq 80\%$ power to detect an odds ratio of 0.4 or lower for adequate cord blood antibody level in newborns from obese versus non-obese mothers, at $\alpha=0.025$.

Statistical Analyses.

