Specific Aim 1. Effects of stress on maternal antibody responses will be tested independently for each vaccination year. Thus, our data will provide valuable data regarding the extent to which effects of stress are consistent and reproducible across flu seasons. We will test the association between obesity and maternal antibody responses using data across all three vaccination years. The primary and supporting endpoints will be the same as above. The independent variable will be obesity status. A secondary analysis will explore the interaction between obesity and stress; these analyses will focus on depressive symptoms and the composite stress measure (CES-D, PSS, and STAI). We expect that stress and obesity will interact, with more pronounced effects of obesity among the highly stressed. Although the study is not specifically powered for the detection of interaction effects, based on our preliminary findings we expect to obtain useful estimates.

Specific Aim 2. The primary analysis will be logistic regression testing whether stress and obesity are associated with attenuated cord blood antibody levels. The primary endpoint will be adequacy of cord blood antibody level (yes/no), with an adequate antibody level defined as a serum HAI antibody titer > 40 . The same models will be used as described in Specific Aim 1, except for the change in dependent variable. A supporting analysis will test cord blood antibody levels as a continuous measure. Linear regression models will be used to test this supporting outcome, using the same independent variables as the logistic regression models.

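### Aim 1 names neither season nor pre-vaccination titre: add season to the pooled obesity models, and for each hypothesis fix one tested odds ratio, with the other handling of starting titre as a prespecified sensitivity analysis

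*Combined protocol and SAP*

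**What the plan says.** Under Sample size calculation (III.E), Aim 1 is powered on an "odds ratio of 0.4 for 4-fold antibody increase" per SD of composite stress with 60 women in a year, and on 0.38 for obese against non-obese women with 180 over three years. Both use α = 0.025, and Holm's procedure is planned for the analysis. Both effect sizes are attributed to preliminary data, without saying whether they were adjusted.

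The Specific Aim 1 text writes out no model. For stress: "Effects of stress on maternal antibody responses will be tested independently for each vaccination year". For obesity, the three years are pooled and "The independent variable will be obesity status". For outcomes: "The primary and supporting endpoints will be the same as above", although the current text above it contains no such definition. Specific Aim 2 then says "The same models will be used as described in Specific Aim 1, except for the change in dependent variable".

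The only additions named anywhere are race and, in one mediational pathway, weeks from vaccination to delivery. Visit 1 (III.D) draws blood before the vaccine is given, so a starting titre can be measured. On eligibility (III.B): "Exclusion criteria are fetal anomaly, health conditions or medications with a major immune component"; earlier influenza vaccination or infection is not mentioned. On vaccine supply (III.C): "All women vaccinated during the same influenza season will receive the vaccine from the same manufacturer and same lot whenever possible". That aims at uniformity within a season, not between seasons.

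**The concern.** A 4-fold rise is a ratio to the starting titre. It is free of starting titre only if log post-titre rises one-for-one with log pre-titre. If it rises less, women who start high are less likely to reach a 4-fold rise. Nothing in the design makes starting titres alike across levels of stress or obesity. A difference in prior immunity could therefore pass for an exposure effect or hide one.

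Season raises a similar problem for the pooled obesity analysis. Strains and lots can change by year, so response rates may too. If the obese share also differs between years, a model without season mixes the two. Even if the share is constant, leaving out season pulls the pooled odds ratio toward 1 and costs power.

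Both choices are open in the current text, so they could be settled after the results are seen.

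**Working it through.** **1. The plan's own figures.** For one standardised predictor and no covariate, power = Φ(√(N·p(1−p))·|ln OR| − z). With N = 60, OR 0.4, two-sided α = 0.025 (z = 2.241) and an assumed 50% responders: √15 × 0.916 = 3.549; 3.549 − 2.241 = 1.307; Φ = 90.4%. The stated figure of at least 90% reproduces as an unadjusted calculation. The obesity figure of 82% is reachable: 81.6–83.3% for an obese share of 40–50% and a non-obese response rate of 60–65%. Neither figure is disputed here.

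**2. Season, by direct arithmetic.** Assume 60 women a year, response of 30/50/70% over the three years, an obese share of 30/40/50%, and no obesity effect within any year.
- Obese: 18×0.3 + 24×0.5 + 30×0.7 = 38.4 responders of 72.
- Non-obese: 42×0.3 + 36×0.5 + 30×0.7 = 51.6 of 108.
- Pooled OR = (38.4/33.6)/(51.6/56.4) = 1.25, although every yearly OR is 1.
- Reversing the drift (50/40/30%): (33.6/38.4)/(56.4/51.6) = 0.80.

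Now let the yearly OR be 0.38, with 30/50/70% response in non-obese women. Response in obese women is then 14.0/27.5/47.0%.
- Constant obese share: the obese average is 29.5% against 50.0%, so the pooled OR is 0.419/1 = 0.42.
- Share of 30/40/50%: obese responders are 18×0.140 + 24×0.275 + 30×0.470 = 23.2 of 72, so the pooled OR is (23.2/48.8)/(51.6/56.4) = 0.52.

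Simulated, to within about a point:

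| Scenario (n = 180) | Without season | With season |
|---|---|---|
| OR 0.38, constant share, power | 69% | 74% |
| OR 0.38, share 30/40/50%, power | 43% | 73% |
| No effect, share 30/40/50%, rejection | 5.9% | 2.2% |

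**3. Starting titre, the mechanism.** If log post = a + b·log pre + error, then log fold rise = a + (b − 1)·log pre + error. Starting titre drops out only at b = 1. Assume a log2 pre-titre SD of 1.6, residual SD 1.3, 50% responders and 40% obese. A correlation r with obesity then means a difference in mean log2 pre-titre of 1.6r/√(0.4×0.6). That is 0.33 (about 1.25-fold) at r = 0.1 and 0.98 (nearly two-fold) at r = 0.3.

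**4. Starting titre, no true effect and no assay noise, slope b from 0.3 to 0.7.**

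| r | Stress unadjusted (n = 60) | Obesity unadjusted (n = 180) | Adjusted, either |
|---|---|---|---|
| 0.1 | 2–3% | 3–6% | 2–3% |
| 0.3 | 5–13% | 13–44% | 2–3% |

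The sign of r sets the direction. Positive r pushes the unadjusted odds ratio below 1, as hypothesised. Negative r pushes it above 1, so false rejections fall on the opposite side and a true effect is masked. For obesity at slope 0.3, unadjusted power is 57/33/12% at r = −0.1/−0.2/−0.3.

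**5. The same check when the slope shortfall is assay noise** (observed slope 0.7, r = 0.3, no true effect). If all of it is noise, the unadjusted tests hold at 2–3%. The adjusted obesity OR is then 1.50 with 14% rejection, and the adjusted stress OR is 1.24 with 5%. If half is noise, the two obesity odds ratios are 0.83 and 1.20, and each test rejects about 5%.

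**6. Precision.** With r = 0, no noise and slopes 0.3–0.7, adjusting gains roughly 2–12 points of power at 50% responders, and nothing at slope 1.

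**The case against.** The strongest reply is that Aim 1 prints no model. Its reference to endpoints given above points to text not in this document, so pre-titre is unnamed, not refused. That stands. If a fuller model exists elsewhere, copying it in would settle much of the point. The supporting endpoints mentioned may also already include a continuous analysis.

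Second, every titre input in the working is assumed. That also stands. A reader might take the mediational pathway on maintenance of maternal antibody as evidence that stress or obesity is correlated with starting titre. It is not: that pathway covers decay from one month after vaccination to delivery, and it is not among the two pathways the plan expects to matter most. If poorer maintenance did carry back to starting titre, r would be negative, which works against the hypothesis.

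Third, a reader might infer that the titre-adjusted odds ratio is the correct one. The documents do not support this. The exposures are not randomised, and starting titre may already carry a long-standing effect of stress or obesity. The assay section gives no precision for the reading ("Titers were determined by identifying the serum dilution at which the titration curve became asymptotic"), and step 5 shows adjustment misleading when the shortfall is noise.

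Fourth, it is tempting to call a result robust only if both odds ratios are significant. That rule is capped by the weaker test. For obesity at slope 0.3 and r = −0.1/−0.2/−0.3 it finds a true effect 56/32/12% of the time, against 91/92/89% for the adjusted test. It also leaves unclear which p-value enters Holm's procedure.

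**Conclusion.** The point holds as a gap in the stated analysis and is worth fixing. It is not a demonstrated bias, and it does not show the power figures to be wrong. Season is missing from the pooled obesity analysis, and the handling of starting titre is not fixed for either Aim 1 exposure.

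The season effect needs response rates that differ by year; bias under no effect also needs an obese share that differs by year. Under the assumed 30/50/70% pattern, leaving season out costs about 5 points of power, or 30 with upward drift in the obese share. The starting-titre effect needs a slope below 1 that is not all assay noise and, for bias, a correlation with exposure. At r = 0.1 it is small; at 0.3 it can be large, especially for obesity. The documents do not say which case applies. They therefore support fixing the choice in advance, not preferring one odds ratio.

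**What to change.** 1. Add season as a covariate in the pooled three-year obesity models.
2. For each Aim 1 hypothesis, name in advance the one odds ratio that supplies the Holm p-value. Report the other version (with or without log pre-vaccination titre, same strain and same assay) as a prespecified sensitivity analysis. State that a difference in direction or significance will be reported as dependence on the handling of starting titre. Say which version the preliminary 0.4 and 0.38 represent.
3. State that the pre-titre covariate belongs to Aim 1 only. Otherwise Aim 2's reuse of the Aim 1 models would carry it into the cord blood analysis, where the endpoint is an absolute titre threshold and the plan is after overall effects on the newborn.

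The cost is SAP wording, with no new visits or blood. Season uses two degrees of freedom. The adjusted odds ratio is conditional and may not be comparable with the preliminary values: in simulation it was 0.25–0.35 where the unadjusted median was 0.37–0.39. Adjustment can also mislead. If the slope shortfall is all noise, with a true effect and r = +0.2, it lowers obesity power from 80% to 56%. That is why both versions are reported and neither is presented as the correct answer.

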Although stress has been studied in association with response to other vaccines including, but not limited to, hepatitis B ⁸ and pneumococcal pneumonia ⁹ assessment of antibody response to influenza vaccination is an ideal model for exploring stress and immune function during pregnancy. As noted, this vaccination that is recommended to pregnant women ¹⁰. Furthermore, the effectiveness of influenza vaccination in pregnant women has important health implications; influenza is more likely to result in serious medical complications among pregnant women than the general population. Relatedly, pregnant women are more likely to undergo hospitalization as a result of influenza than non-pregnant individuals of similar age. Therefore, understanding the effects of stress on response to this particular vaccine has important implications for potentially severe health outcomes. **The primary goal of this investigation is to examine whether pregnant women who report greater life stress show poorer antibody responses to influenza vaccination measured at one month post-vaccination and poorer antibody transfer to the neonate as measured in cord blood at the time of delivery. This study will also examine the role of obesity in these relationships. It is predicted that obesity will exacerbate effects of stress, resulting in the poorest outcomes in women with high stress and obesity.**

III. PROCEDURES

A. Research Design

The current study is designed to evaluate the relationship between psychosocial factors on one hand and antibody responses to influenza vaccination on the other. Participants will complete two study visits: pre-

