Visit 1 will take 60-90 minutes. You will answer questionnaires about your health, health behaviors, stressful life events, mood (e.g., anxiety and depressive symptoms), and social support. These include questions about positive and negative interactions with your friends/family as well as questions regarding stressful or traumatic events you may have experienced growing up. You will have 35 mL of blood drawn. Finally, you will receive an influenza virus vaccination (flu shot).

Visits 2 will take about 30 minutes and will occur one month after Visit 1. You will answer questions about your recent health behaviors, life stress, and mood and have 30 mL of blood drawn.

During your hospital stay at the time of the delivery of your baby, hospital staff will obtain a 30mL blood sample for our study. If this sample is not collected during your hospital stay, or if you do not deliver in a hospital, we will schedule a visit to your home or at our office soon after your delivery at a time that is convenient for you in order to collect this blood sample.

Finally, cord blood is standardly collected at every delivery at OSUMC. If it is not needed for medical reasons, it is discarded after a few days. If you deliver at OSUMC and your baby's cord blood is not needed for medical reasons, it will be given to our study personnel rather than being thrown away. If cord blood is not available for your baby, we will schedule a visit to our office soon after your delivery at a time that is convenient for you, in order to collect this blood sample. If you cannot come to our office, we will work with you to schedule a visit to your home. This blood sample will be collected from your baby by heel stick which is similar to a finger stick in adults.

Also, after your delivery, researchers will access your medical records to obtain the following information related to your pregnancy: your date of delivery, the birth weight and sex of your baby, how much weight you gained during your pregnancy, your blood pressure at clinic visits, the results of your clinical screenings for sexually transmitted diseases, and whether you had any complications during pregnancy or delivery.

Use of REDCap

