Secondary mediational analyses will examine four potential pathways linking stress and obesity with low cord blood antibody titers: 1) the magnitude of maternal response at one month post-vaccination, 2) the maintenance of maternal antibody levels over time (maternal antibody at one month post-vaccination / maternal antibody at delivery) controlling for weeks from vaccination to delivery, 3) efficiency of antibody transfer (ratio of maternal antibody at time of delivery / newborn antibody level), and 4) the frequency of preterm birth (expected to be 15% overall). We expect factors 1 & 3 to exert the greatest effects. Our study is powered to detect overall effects of maternal stress and obesity on newborn antibody levels, but is not powered to detect the relative influence of each of these specific pathways. However, these analyses will provide a critical foundation for future studies in this line of investigation which will include this focus.

We do not expect racial differences in Aim 1. Due to higher rates of preterm birth in Blacks than Whites (18% vs 12%), this pathway is likely to contribute more strongly to the association between stress and lower cord blood titers for Blacks. We will use two approaches to examine effects of race: 1) inclusion of race as a predictive variable and 2) testing the secondary analysis model above separately for Blacks and Whites.

References

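### Women who deliver before Visit 2 give a mistimed mediator in pathway 1 and, usually, a reversed maintenance ratio in pathway 2

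*Combined protocol and SAP*

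**What the plan says.** - **Eligibility (III.B, Sample).** Enrolment is open to "adult (18 years and older) pregnant women who choose to have the influenza vaccination and who give informed consent". The exclusions are: "Exclusion criteria are fetal anomaly, health conditions or medications with a major immune component (e.g., arthritis, cancer, lupus) and inability to give informed consent". Neither list mentions gestational age or time to expected delivery.
- **Timing (III.D, Detailed Study Procedures).** The vaccine is given at Visit 1. Visit 2 "will occur one month after Visit 1". It is not tied to the date of delivery.
- **Outcome (II, Background and Significance).** The interest is in "poorer antibody transfer to the neonate as measured in cord blood at the time of delivery".
- **Maternal delivery sample (III.A and III.D).** It is drawn during the hospital stay. If missed, it may be drawn later at home, at a study site or, under III.A, at a post-partum appointment.
- **Mediation (III.E, Specific Aim 2).** Pathway 1 is "the magnitude of maternal response at one month post-vaccination". Pathway 2, maintenance, is the ratio "maternal antibody at one month post-vaccination / maternal antibody at delivery) controlling for weeks from vaccination to delivery". Pathway 4 is preterm birth, expected in 15%. The plan expects pathways 1 and 3 to matter most and says that the study is not powered to separate the pathways.

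No section says how a woman who delivers before Visit 2 is scheduled or analysed.

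**The concern.** A mediator should be measured before the outcome that it is meant to explain. Nothing in the plan secures that order for pathways 1 and 2. For a woman vaccinated less than about a month before delivery, the value entered for pathway 1 describes a response that had not finished developing when the cord blood was taken. The value entered for pathway 2 can carry the opposite meaning from its label. This is more than missing detail, because the stated definitions applied as written give a wrong score for these women.

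Two of the four pathways are at stake, one of them among the two expected to matter most. The plan presents these analyses as the basis for later studies. The affected women are also not a random subset, since early delivery makes the reversal more likely and preterm birth is pathway 4.

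**Working it through.** **1. Order of samples.** Let V be vaccination (Visit 1), V + 1 month be Visit 2, and D be delivery, when cord blood is taken.

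- If D is later than V + 1 month, the order is mediator then outcome, as intended.
- If D is earlier than V + 1 month, the order is outcome then mediator. Nothing in III.B or III.D rules this out.

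**2. The maintenance ratio.** Write R = A1 / AD, with A1 the antibody at Visit 2 and AD the maternal antibody at delivery.

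- Intended order: a decline after Visit 2 gives AD < A1, so R > 1. A larger R means more loss.
- Delivery first, AD drawn at delivery, titre still rising: A1 > AD, so again R > 1. A larger R now means a stronger rise, yet it is scored as more loss.
- Delivery first, AD drawn late under the fallback and after Visit 2: R is not reversed, but AD is no longer a delivery value.

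**3. The weeks covariate.** It is stated for pathway 2 only. When D falls exactly at V + 1 month, both samples coincide and R = 1. If titres rise up to one month and fall afterwards (an assumption; the documents give no time course), R tends to exceed 1 on both sides of that point. A linear term in weeks cannot follow that shape. A flexible term would adjust the average R but would not change what an individual woman's R means.

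**4. Share affected.** The documents give the 15% preterm rate but no distribution of gestational age at vaccination. Assumptions: vaccination uniform over the weeks shown, among women still pregnant; 15% of deliveries uniform over weeks 32–37 and the rest over weeks 37–41; one month = 30/7 = 4.29 weeks.

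| Vaccination weeks (assumed) | Deliver before Visit 2 | Of 180 |
|---|---|---|
| 0–40 | 11.0% | 20 |
| 8–40 | 13.8% | 25 |
| 20–40 | 23.0% | 41 |
| 8–36 | 6.4% | 11–12 |
| 8–32 | 1.1% | 2 |
| 8–28 | about 0% | 0 |

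Hand check for delivery at week 39 with no upper limit on vaccination week: share = 4.29 / (39 − first week). This gives 4.29/39 = 11.0%, 4.29/31 = 13.8% and 4.29/19 = 22.6%, in line with the first three rows.

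**5. Would restricting the primary Aim 2 set be a better remedy?** First reproduce the plan's figure. For one standardised covariate in logistic regression, power = Φ(√(n·p·(1−p))·|ln OR| − z). Take n = 60, OR = 0.45, two-sided α = 0.025 (z = 2.241) and p = 0.5. Sidedness and p are not stated, so both are assumptions. Then √15 × 0.7985 = 3.093, and Φ(3.093 − 2.241) = 80.3%, against the stated 80% or more. With smaller sets:

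- n = 54 (10% removed): Φ(2.934 − 2.241) = 76%
- n = 49 (about 18% removed): Φ(2.795 − 2.241) = 71%

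A rule that keeps women whose due date (week 40) is at least 5 weeks after vaccination was also simulated. Here vaccination was uniform from week 6, 12 or 20 up to week 36 or 39; 15% of deliveries were uniform over weeks 32–37 and the rest normal with mean 39.3 and SD 1.1, held within weeks 37–42. The rule removes about 3–18% of women, and about 3–6% of those kept still deliver before Visit 2, most of them preterm.

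**The case against.** **Reach.** The fault lies in two secondary pathways that the plan itself calls unpowered. A reader might infer that the primary Aim 2 result is corrupted as well. The documents do not support that: the primary model relates cord adequacy to stress and obesity and does not use the Visit 2 sample. Newborns delivered soon after vaccination may have low cord titres for that reason alone. That would confound the primary result only if vaccination timing were related to stress or obesity, and no such link is shown. Without one, it adds outcome variation and perhaps some attenuation. This objection stands.

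**Bias.** A reader might infer that the indirect effects are biased by a known amount or in a known direction. Neither can be shown. The cord titre does not plausibly alter the mother's later response, so the late pathway 1 value is a poorly timed measure rather than reverse causation. That stands too, but it does not rescue the scoring of pathway 2.

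**Not every ratio is reversed.** The late-sample fallback means that some affected women have a delivery sample drawn after Visit 2. This stands, and pathway 2 therefore needs its own condition on sample order.

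**The remedy selects on delivery date.** Keeping only women whose Visit 2 precedes delivery conditions on something that overlaps pathway 4, and could itself distort pathways 1 and 2. This is the most serious objection to the fix. It calls for a report of who is excluded and a second set defined from Visit 1 information. It does not justify leaving the reversed values in.

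**Conclusion.** The concern holds for pathways 1 and 2. For women who deliver before Visit 2, the plan's definitions give a mediator measured after its outcome. Unless the maternal delivery sample was also late, they give a maintenance ratio in which a rising titre counts as loss. That follows from the text and needs no assumption beyond a titre still rising between delivery and Visit 2.

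The number of such women is not in the documents. The range of about 0–23% (0 to 41 of 180) rests on assumed uniform vaccination timing, and it is near zero if vaccination in practice stops by about week 32. The figures are illustrative.

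The finding does not extend to the primary Aim 2 analysis. Restricting that set would be a poor trade: at an assumed 50% event rate and unchanged effect, power per year drops from 80% to roughly 71–76% if 10–18% of women are removed, and some early deliverers would remain.

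**What to change.** Leave enrolment, vaccination and the visit schedule unchanged. In III.E, Specific Aim 2, secondary mediational analyses:

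1. Limit pathways 1 and 2 to women whose Visit 2 sample predates delivery. For pathway 2, also require that it predates the maternal delivery sample.
2. Report the number excluded, broken down by stress, obesity and preterm status.
3. As a sensitivity analysis, repeat pathways 1 and 2 in women whose due date, recorded at Visit 1, is at least 5 weeks after vaccination. This set does not depend on the actual delivery date, though it will still contain some women with reversed order. The two analyses have different weaknesses and should be read together.
4. Keep the primary Aim 2 set as planned. Apply the due-date restriction there only as a sensitivity analysis.

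The cost is a few lines of SAP text, recording the due date and the sample dates, and a somewhat smaller sample in two secondary analyses that are already unpowered.
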